#### **4.1.3. Combination Dose-Finding (Part 3)**

Part 3 enrollment will be initiated after the MTD has been determined in Part 1 and will include dose-finding to evaluate safety and tolerability of the combinations. Enrollment of Part 3 will occur in parallel with Part 2. Dose-finding will use a 3 + 3 design to evaluate different doses of INCB059872 in combination with other therapies in the following treatment groups:

- Combination TG C: INCB059872 in combination with ATRA in subjects with relapsed/refractory AML. The starting dose for INCB059872 in this cohort will be 2 mg QD (2 dose levels below the recommended dose for monotherapy expansion in TG A1).
- Combination TG D: INCB059872 in combination with azacitidine in subjects with newly diagnosed, treatment-naive AML or MDS with at least 5% bone marrow blasts and IPSS-R intermediate or higher risk disease who are unfit to tolerate standard intensive chemotherapy at study entry and who are eligible to receive azacitidine as first-line therapy for the disease under study. The starting dose for INCB059872 in

this cohort will be 2 mg QD (2 dose levels below the recommended dose for monotherapy expansion in TG A1).

- Combination TG E: INCB059872 in combination with nivolumab in subjects with advanced SCLC who previously progressed on platinum-based treatment. The starting dose for INCB059872 in this cohort will be 3 mg QOD (the recommended dose for monotherapy expansion in TG B1).

The starting dose of INCB059872 in the combination treatment groups was based upon the tolerability of INCB059872 monotherapy identified in Part 1 of this study. Doses of the combination agents will be selected from conventional dose regimens and will remain the same for all dose-finding and dose-expansion cohorts. INCB059872 doses will not exceed the monotherapy MTD identified in Part 1. A minimum of 3 subjects will initially be enrolled in each treatment group in Part 3, and each subject will be observed for a DLT observation period of 1 cycle (28 days) before the next dose cohort or expansion to Part 4 begins enrollment. Subjects must have taken at least 75% of the cohort-specific dose (at least 11 doses for QOD schedule or at least 21 doses for QD schedule) in the first 28 days of study treatment or have had a DLT to be considered evaluable. Subjects who are not evaluable will be replaced.

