### **4.3.2. Replacement of Subjects**

In Parts 1 and 3, if a subject is not evaluable (ie, did not receive at least 75% of cohort-specific dose within the first 28 days of study treatment), another subject will be enrolled at this dose level. Subjects who report DLTs will be considered evaluable for the purpose of determining the safety and tolerability of the dose.

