### 5.4.3. Dose-Limiting Toxicity and Determination of Maximum Tolerated Dose of INCB059872

Dose-limiting toxicity will be defined as the occurrence of any of the toxicities in Table 4 occurring up to and including Day 28, except those with a clear alternative explanation (eg, disease progression) or transient ( $\leq$  72 hours) abnormal laboratory values without associated clinically significant signs or symptoms based on investigator determination. All DLTs will be assessed by the investigator using CTCAE v4.03 criteria (NCI 2010). Subjects who receive at least 75% of the planned doses (eg, 11 of 14 doses for QOD schedule) of study drug at the level assigned or have a DLT will be considered evaluable for determining tolerability of the dose. Subjects who cannot complete 75% of the planned doses of study drug for reasons not due to toxicities related to study drug will not be considered evaluable for the purposes of determining the MTD and will be replaced.

Individual subject dose reductions may be made based on events observed at any time during treatment with study drug; however, for the purposes of dose cohort escalation/de-escalation, expanding a dose cohort, and determining the MTD of INCB059872, decisions will be made based on events that are observed from the first day of study drug administration through and including the final day of Cycle 1 (Day 28). A lower MTD may subsequently be determined based on relevant toxicities that become evident after Day 28.

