**Table 4: Definition of Dose-Limiting Toxicity**

Nonhematologic toxicity

Any <math>\geq</math> Grade 3 nonhematologic toxicity EXCEPT:

Transient (<math>\leq</math> 72 hours) abnormal laboratory values without associated clinically significant signs or symptoms.

Nausea, vomiting, and diarrhea adequately controlled with medical therapy within 48 hours.

An event clearly associated with the underlying disease, disease progression, a concomitant medication, or comorbidity.

Singular or nonfasting elevations in blood glucose (ie, blood glucose excursions will be considered toxicities if fasting blood glucose is elevated on 2 separate occasions).

Hematologic toxicity

Anemia : Grade 4, unexplained by underlying disease

Neutropenia:

For solid tumors: Grade 4 that does not recover to <math>\leq</math> Grade 3 in <math>\leq</math> 7 days after dose interruption.

For AML/MDS/MF: Grade 4 with a hypocellular bone marrow lasting <math>\geq</math> 6 weeks after the start of a course in the absence of residual disease.

Febrile neutropenia (for solid tumors only): absolute neutrophil count <math>< 1.0 \times 10^9/L</math> with a single temperature of <math>> 38.3^\circ C</math> (<math>101^\circ F</math>) or a sustained temperature of <math>\geq 38^\circ C</math> (<math>100.4^\circ F</math>) for more than 1 hour.

Thrombocytopenia:

For solid tumors: Any Grade 4 or Grade 3 with bleeding or any requirement of platelet transfusion.

For AML/MDS/MF: Grade 3 or higher with clinically significant bleeding or any requirement of platelet transfusion outside of institutional practice.

Other toxicities not meeting criteria above

While the rules for adjudicating DLTs in the context of dose escalation are specified above, an AE not listed above may be defined as a DLT after a consultation with the sponsor and investigators, based on the emerging safety profile.

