#### **5.4.6. Procedures for Cohort Review and Dose Escalation**

Telephone conferences will be scheduled by the sponsor with study investigators in order to review cohort-specific data and overall safety data, to agree on dose escalation, adjudicate individual high-grade AEs as potentially dose-limiting, and guide other major study decisions.

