#### 5.4.8. Management of Immune-Related Adverse Events

Nivolumab is considered an immune modulator, and it is possible that irAEs (both nonserious and serious) may occur. Adverse events of a potential immunologic etiology or irAEs may be defined as an AE consistent with an immune phenomenon associated with drug exposure *after all other etiologies have been eliminated*. Immune-related AEs may be expected based on the nature of the study treatment, their mechanism of action, and reported experience with these and other immunotherapies. Special attention should be paid to AEs that may be suggestive of potential irAEs. An irAE can occur shortly after the first dose or several months after the last dose of treatment. Suspected irAEs should be discussed with the medical monitor when possible.

Subjects should receive appropriate supportive care measures as deemed necessary by the treating investigator. Suggested supportive care measures for the management of drug-related AEs with potential immunologic etiology are outlined in [Table 6](#). Detailed supportive care guidelines for specific irAEs can be found in [Appendix H](#). Nivolumab may have specific irAE management guidelines within the package insert; the treating investigator may use labeled guidance or institutional guidelines for the management of irAEs if preferred. For each AE, attempts should be made to rule out other causes, including but not limited to metastatic disease or bacterial or viral infection, which might require specific supportive care.

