**Table 6: General Approach to Handling Immune-Related Adverse Events**

irAE	Withhold/Discontinue Nivolumab and INCB059872	Guidance for Restarting Study Treatment	Supportive Care
Grade 1	No action.	Not applicable.	Provide symptomatic treatment.
Grade 2	Withhold nivolumab. May withhold INCB059872 per investigator's discretion. Discontinue if unable to reduce corticosteroid dose to < 10 mg/day of prednisone or equivalent within 6 weeks of toxicity.	May return to treatment if improves to Grade 1 or resolves within 6 weeks. If AE resolves within 4 weeks, subject may restart at the same dose and schedule for both nivolumab and INCB059872. For an AE that does not resolve within 4 weeks, nivolumab should be reduced 1 dose level but INCB059872 may be restarted at the same dose and schedule. If AE does not resolve within 6 weeks, study treatment with both study drugs should be discontinued or discussed with medical monitor.	Consider systemic corticosteroids in addition to appropriate symptomatic treatment.
Grades 3	Withhold or discontinue nivolumab and INCB059872. Discontinue if unable to reduce corticosteroid dose to < 10 mg/day of prednisone or equivalent within 6 weeks of toxicity.	Any restart of study treatment must be discussed with medical monitor before restarting treatment.	Systemic corticosteroids are indicated in addition to appropriate symptomatic treatment. May use 1 to 2 mg/kg of prednisone or equivalent per day. Steroid taper should be considered once symptoms improve to $\leq$ Grade 1 and tapered over at least 4 weeks in most cases.
Grade 4	Discontinue nivolumab and INCB059872.	Not applicable. Any exceptions require medical monitor approval.	Systemic corticosteroids are indicated in addition to appropriate symptomatic treatment. May use 1 to 2 mg/kg prednisone or equivalent per day. Steroid taper should be considered once symptoms improve to $\leq$ Grade 1 and tapered over at least 4 weeks in most cases.

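### In TG E, DLT evaluability counts INCB059872 doses only, and the protocol's replacement rules disagree on subjects who fall short because of toxicity

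*Protocol*

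**What the plan says.** **Which doses count.** Protocol 4.1.3 makes a Part 3 subject evaluable if there is a DLT, or if intake over the 28 days of Cycle 1 was "at least 75% of the cohort-specific dose (at least 11 doses for QOD schedule or at least 21 doses for QD schedule". Anyone else is replaced. Section 4.1.1 has the same rule for Part 1, and 5.4.3 repeats the 11-of-14 example. Protocol Section 5 plans 14 INCB059872 doses per QOD cycle and 28 per QD cycle. SAP 4.1.5 places nivolumab on Day 1 and Day 15. SAP 5.3 defines no DLT-evaluable set, and SAP 9.2.2 only lists DLTs. The partner regimen is meant to be fixed: "Doses of the combination agents will be selected from conventional dose regimens and will remain the same for all dose-finding and dose-expansion cohorts".

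**What happens to a nivolumab hold.** For a Grade 2 immune-related event (irAE), Table 6 says "Withhold nivolumab. May withhold INCB059872 per investigator's discretion". Section 5.4.8 introduces that table as "Suggested supportive care measures for the management of drug-related AEs with potential immunologic etiology" and lets the investigator use label or institutional guidance instead. In Table 4, listed nonhematologic DLTs start at Grade 3. For anything else, "an AE not listed above may be defined as a DLT after a consultation with the sponsor and investigators". Among the tasks of the cohort review, 5.4.6 names the need to "adjudicate individual high-grade AEs as potentially dose-limiting".

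**Who is replaced.** Section 4.3.2 treats as not evaluable, and replaces, a subject who "did not receive at least 75% of cohort-specific dose within the first 28 days of study treatment", whatever the reason, unless a DLT was reported. Section 5.4.3 restricts this to "Subjects who cannot complete 75% of the planned doses of study drug for reasons not due to toxicities related to study drug".

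**The concern.** The Part 3 objective is a recommended dose of the combination. In TG E the DLT window holds two planned nivolumab infusions, and the second is the one most likely to be lost when an early immune-related event appears. If evaluability ignores nivolumab, a dose can be cleared on subjects who did not receive the combination as planned, and the event behind the missed infusion need never be put to a DLT decision. TG E also starts at 3 mg QOD, the full recommended solid-tumor dose, whereas TG C and TG D start two levels below theirs. Part 3 plans about 15 subjects over all three groups, and a recommended dose opens E1 with about 30.

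The replacement rule raises a related problem in every Part 1 and Part 3 group. A subject who cannot keep taking the drug because of its toxicity, without meeting a DLT definition, carries information about tolerability. Replacing that subject removes the information from the escalation decision.

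**Working it through.** **1. The plan's own figures.** 0.75 × 14 = 10.5, rounded up to 11; 0.75 × 28 = 21. Table 11 follows from f(x) = (1 − x)³ + 3x(1 − x)⁵, which gives 90.6%, 70.9%, 49.4%, 30.9%, 17.2% and 8.2% at true DLT rates of 10% to 60%. All six values reproduce.

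**2. Whose doses the counts are.** A 28-day window holds 2 nivolumab infusions, so counts of 11 and 21 can only refer to INCB059872. Table 6 does refer to nivolumab and INCB059872 together as both study drugs, so the words study drug in 5.4.3 are slightly ambiguous, but its 11-of-14 example is not. Applied to nivolumab, the same 75% would require 0.75 × 2 = 1.5, rounded up to 2 of 2.

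**3. The Day 15 hold.** QOD dosing on Days 1, 3, …, 27 gives 7 doses before Day 15, so 4 of the remaining 7 reach 11. A subject with Day 15 nivolumab withheld and INCB059872 continued can have 11/14 = 78.6% of one drug and 1/2 = 50% of the other, and is evaluable. A 0-of-3 cohort can be cleared on 33 of 42 INCB059872 doses and 3 of 6 infusions. If INCB059872 also stops from Day 15, the subject has 7 doses and is not evaluable, so the gap concerns the nivolumab-only hold.

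**4. Illustrated size of the missed infusion.** The documents give neither a miss rate nor the share of DLT risk tied to the second infusion. Assume that a fraction m of subjects miss Day 15 without a DLT, that a share h of DLT risk depends on that infusion, and that the true rate on full dosing is p = 30%. Clearance is then f(p(1 − mh)), against f(0.30) = 49.4%. The chance that a 3-subject cohort contains at least one such subject is 1 − (1 − m)³.

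| m (assumed) | Cohorts of 3 with at least one | Clearance, h = 25% | Clearance, h = 50% |
|---|---|---|---|
| 5% | 14.3% | 50.2% | 51.0% |
| 10% | 27.1% | 51.0% | 52.5% |
| 20% | 48.8% | 52.5% | 55.7% |

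Last cell: 0.30 × (1 − 0.20 × 0.50) = 0.27, and f(0.27) = 0.389 + 0.168 = 0.557. At p = 20% and h = 50%, clearance is 71.9%, 73.0% and 75.2%, against 70.9%.

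**5. The replacement rules, applied to one subject.** Table 5 holds INCB059872 in solid tumors for asymptomatic platelets of 25 to below 50 until they recover to at least 75, then restarts at a lower dose. Table 4 makes solid-tumor thrombocytopenia a DLT at Grade 4, at Grade 3 with bleeding, or if platelets are transfused. Taking 25 to below 50 as Grade 3, this subject has no DLT. Four missed QOD doses leave 10/14 = 71.4%, below threshold.
- Under 4.1.1, 4.1.3 and 4.3.2 the subject is replaced. If the other two and the replacement have no DLT, the cohort reads 0 of 3, although 4 subjects were treated.
- Under 5.4.3 the subject does not meet the evaluable sentence (75% or a DLT), but the replacement sentence does not apply either, because drug toxicity caused the shortfall. No status is given.

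**6. SAP nivolumab dose intensity.** SAP 6.4.4 sets the assigned dose at 3 × (⌈S/28⌉ + ⌈(S − 14)/28⌉), with S the last infusion day. Day 1 only: S = 1, 3 × (1 + 0) = 3 mg/kg, so 3/3 = 100%. Day 1 and Day 29: S = 29, 3 × (2 + 1) = 9, so 6/9 = 66.7%. A missed Day 15 infusion lowers this figure only if dosing resumes.

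**The case against.** **Oversight is likely to see such holds.** The high-grade clause in 5.4.6 is one item in a wider task that also covers cohort-specific and overall safety data. Section 5.4.8 asks that suspected irAEs be discussed with the medical monitor when possible. Section 8.7 provides regular sponsor and investigator meetings and an internal safety board. Section 5.4.3 allows a lower MTD on later toxicity, and 4.1.3 allows a tolerable cohort to grow to 12. All this stands. A Grade 2 hold would ordinarily be known to those who clear the dose, but nothing obliges them to decide whether it is a DLT.

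**The scenario is narrow.** A Grade 3 or higher irAE is generally already a DLT under Table 4, and Table 6 then holds both drugs. This also stands, and it limits the size of the problem.

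**The replacement sections mostly agree.** Sections 4.1.1, 4.1.3, 4.3.2 and the first evaluability sentence of 5.4.3 are consistent, so only the replacement sentence of 5.4.3 differs. That is fair as a matter of reading. But the majority reading is the one that removes toxicity-driven shortfalls from the denominator, so the difference is more than wording.

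**The SAP would hide the missed infusion.** A reader might infer this from the 100% dose intensity. The documents do not support it: SAP 6.4.4 also counts subjects with nivolumab interruptions, and Appendix A includes Table 3.2.23 (events leading to partner-drug interruption), Table 3.2.26 (irAEs), and Listings 2.7.1 and 2.7.8. An end-of-study summary does not drive cohort clearance in any case.

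**Conclusion.** Both points hold on the text. In TG E, the stated rules can count a subject as an evaluable non-DLT after half of the planned nivolumab, with only a discretionary route to a DLT decision. In Parts 1 and 3, following 4.3.2 takes subjects who fall short because of drug toxicity out of the 3 + 3 denominator, which the replacement sentence of 5.4.3 does not do.

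The size cannot be derived from the documents. On the assumed inputs above, the missed infusion raises clearance at a 30% DLT rate by 0.8 to 6.3 percentage points (50.2 − 49.4 and 55.7 − 49.4), and the top of that range needs both assumptions at their highest. No figure is available for the replacement rule. Protocol Table 3 notes that all three TG B subjects at 3 mg QD were interrupted and reduced in Cycle 1, so early interruption does occur, although 1.6.2 counts two of that cohort as DLTs.

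Two stronger readings should be resisted. One is that unsafe doses would often be cleared. If 25% to 50% of truly intolerant subjects were recorded as non-DLT, f at a 30% rate would be 65.4% to 81.4%, but nothing in the documents supports such a share. The other is that every Grade 2 irAE hold ought to be a DLT. Table 4 does not say so, and the gap is the absence of a required decision. This is a cheap improvement to a small-sample safety decision, not a defect that invalidates the design.

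**What to change.** 1. **TG E evaluability (4.1.3, 4.3.2, 5.4.3).** Define evaluable as a DLT, or at least 11 of 14 QOD (21 of 28 QD) INCB059872 doses plus both Cycle 1 nivolumab infusions. State a short window for the second infusion around Day 15, so that follow-up remains before the DLT window closes. The ± 2 days already in Table 7 would leave 28 − 17 = 11 days after the latest infusion. If the infusion is later, extend the DLT window.
2. **Replacement (4.1.1, 4.1.3, 4.3.2, 5.4.3).** Replace only subjects whose shortfall, in either drug where there are two, is not due to treatment-related toxicity.
3. **Toxicity shortfalls.** Do not replace these subjects. Require that each be adjudicated as DLT or non-DLT at the 5.4.6 review before the dose is cleared, and count each as evaluable in the denominator whichever way that goes. Widen 5.4.6 from high-grade events to any event that caused such a shortfall.

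The cost is about one sentence in each section. No new data are needed, since 5.3.2 already has infusions documented. The downside is a few replacements, or a cohort expanding from 3 to 6.

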#### **4.1.4. Combination Dose Expansion (Part 4)**

[figure not shown]
Upon identification of the recommended dose(s) for each treatment combination in Part 3, expansion cohorts of approximately 30 subjects in each treatment group may begin enrollment to further determine safety, tolerability, efficacy, PK, [REDACTED] of the selected dose(s).

- Combination TG C1: INCB059872 in combination with ATRA using the regimen identified in Part 3 in subjects with relapsed/refractory AML.
- Combination TG D1: INCB059872 in combination with azacitidine using the regimen identified in Part 3 in subjects with newly diagnosed, treatment-naive AML or MDS with at least 5% bone marrow blasts and IPSS-R intermediate or higher risk disease who are unfit to tolerate standard intensive chemotherapy at study entry and who are eligible to receive azacitidine as first-line therapy for the disease under study.
- Combination TG E1: INCB059872 in combination with nivolumab using the regimen identified in Part 3 in subjects with advanced SCLC who previously progressed on platinum based treatment.

In Part 4, a stopping rule for futility is planned for each combination dose expansion treatment group. The futility analyses for combination TGs will be conducted when 15 subjects for each disease type have been treated and evaluated for response or have permanently discontinued study treatment because of disease progression, withdrawal of consent, or death. The futility

analyses for TG D1 will be conducted when the first 15 subjects with AML or when the first 15 subjects with MDS have been treated.

**Figure 1: Study Design**

## 4.2. Measures Taken to Avoid Bias

This is an open-label study; no comparisons will be made between subjects or against historical controls. Measurements of safety and efficacy are objective measurements, and only comparisons to pretreatment conditions will be made.

## **4.3. Number of Subjects**

### **4.3.1. Planned Number of Subjects**

Approximately 215 subjects will be enrolled in this study as follows:

- Part 1 will enroll approximately 24 subjects into each dose-escalation treatment group. This may vary due to the number of cohorts required to determine the target dose(s).
- Part 2, approximately 15 subjects will be enrolled in each of the 4 treatment groups.
- Part 3 will enroll approximately 15 subjects total for all three treatment groups. This number may vary due to the number of cohorts required to determine the optimal combination dose. The sponsor, in consultation with participating investigators, may elect to expand a dose cohort(s) deemed tolerable, to up to 12 subjects, in order to obtain supplemental PK, [REDACTED], and safety data.
- Part 4 will enroll approximately 30 subjects in TG C1, TG D1, and TG E1.

### **4.3.2. Replacement of Subjects**

In Parts 1 and 3, if a subject is not evaluable (ie, did not receive at least 75% of cohort-specific dose within the first 28 days of study treatment), another subject will be enrolled at this dose level. Subjects who report DLTs will be considered evaluable for the purpose of determining the safety and tolerability of the dose.

## **4.4. Duration of Treatment and Subject Participation**

After signing the ICF, screening assessments may be completed over a period of up to 28 days. Each subject enrolled in the study may continue to receive study treatment in continuous 28-day cycles. If the subject discontinues INCB059872, the treatment period will end and the subject will enter the follow-up period (see Section 6.4). Study participation is expected to average approximately 6 months per individual subject.

## **4.5. Overall Study Duration**

The study begins when the first subject signs the informed consent form. The end of the study will occur when all subjects have discontinued study drug and have completed applicable follow-up assessments.

If there have been  $\leq 2$  subjects on study for more than 6 months, a database lock of the study may occur to allow the analysis of the study data. Any remaining subjects may continue to receive study treatment and be seen by the investigator per usual standard of care for this population. The investigator will be expected to monitor for and report any SAEs, AEs of special interest, and pregnancies, as detailed in Section 8. The remaining subjects are considered to be on study until a discontinuation criterion is met and written notification is provided to the sponsor.

